## Measures

The behavioral measures described below will be obtained at baseline (week 0) and the end of each phase (weeks 2, 4, and 6), except for smartphone EMA, which will be collected daily in each participant's home environment throughout the 6 weeks of study participation. All questionnaires will be administered using MD Anderson's Qualtrics platform. Missed visits and associated assessments will be recorded in the study database, but will not be logged as protocol deviations because they are expected in smoking cessation trials. In our previous tobacco-related trials over the past 20 years, we have found that participants only attend about 75% of scheduled sessions. Refer to **Table 2** for a list of the project measurement domains and assessments.

**COVID-19 adaptation:** We will ask participants to collect and ship their urine samples to us, using postage-paid supplies that we will mail to them (see Appendix BB). Alternatively, community participants may be asked to provide a urine sample at an approved collection site within a week of their scheduled virtual "in-person" visits. Approved sites may include MD Anderson, University of

past) will be collected using the EC items of the Tobacco Products and Risk Perceptions Survey (TPRPS; see Appendix P), a survey developed by the Georgia State University Tobacco Center of Regulatory Science (TCORS). We will also collect participants' exposure to cigarette smoke at home and at social setting using the Environmental Tobacco Smoke Exposure Questionnaire (ETSEQ) at the screening session.

At visits 0, 1, 2, and 3, we will collect self-reported information on hormonal contraception use and menstrual phase (estimated from the start date of the last menstrual period) in premenopausal women. Because withdrawal symptoms may influence product switching, we will examine these factors as potential mediators in our analyses (Exploratory Aim). Both being in the luteal phase, compared to follicular phase, and use of hormonal contraception have been found to increase nicotine withdrawal symptoms. Because these are exploratory factors, we elected to not collect blood at every session for hormonal confirmation using progesterone, or to exclude women with factors that would influence these factors (e.g., being post-hysterectomy or post-menopausal).

**Assessment of product use.** As part of Aims 1 & 2, we will collect measures of CC and EC product use and exposure. At each visit, study staff will complete a Time Line Follow Back (TLFB; see Appendix O) interview to record nicotine product use since their last visit, including daily CC use (all phases; CPD), SREC use (Phases 2 & 3; SREC sessions/day), and other nicotine product use (all phases; including other tobacco and non-study EC products). Participants will be required to return used and unused SREC sealed pods at weeks 4 and 6 for product accounting.

During each phase, participants will provide a urine sample to measure total nicotine equivalents (TNE) and the tobacco minor alkaloids (MA) anabasine and nicotelline, which will be analyzed by [name], associate professor of Integrative Medicine Research at MD Anderson, using liquid chromatography-electrospray ionization-tandem mass spectrometry (LC-ESI-MS/MS). TNE is the sum of total nicotine, cotinine, 3'-hydroxycotinine, and nicotine N-oxide excreted in urine ("total" refers to the analyte and its glucuronide conjugate), comprising 85 to 95% of the nicotine dose received by a tobacco user. Use of TNE will enable us to quantify changes in nicotine exposure throughout the study. The MAs anabasine and nicotelline will allow us to estimate differential use in combustible vs. EC use, because MAs are almost exclusively derived from tobacco, and not nicotine.

During all phases, participants will complete SMS-prompted once daily smartphone Qualtrics assessments of product use (CPD, number of EC episodes [Phases 2 & 3], other tobacco use) and 2 daily random assessments of nicotine dependence symptoms (withdrawal, craving, and affect; see Assessment of Product Reinforcement, below). For the daily assessments of product use, the SMS will arrive on the participant's smartphone approximately 2 hours before his or her self-determined bed time, and will contain a link to a questionnaire provided through MD Anderson's Qualtrics survey platform. The random EMA assessments of nicotine dependence symptoms will be restricted to 2 instances per day to limit participant burden. To do so, each day will be divided into 2 blocks, based on each participant's reported wake and bed time that is collected at the screening visit (see Appendix X). Our SMS/Qualtrics backend software, running on a Microsoft SQL Server, will prevent random assessments from occurring within 2 hours of other assessments. The *primary* outcome measure of Aims 1 & 2, CPD, will come from the smartphone daily diary data of CC use over the past 24 hours. TLFB collected at each phase will be used as a secondary source of CC use to supplement missing smartphone daily diary data.

The total time to complete the once daily product use and 2 random EMA assessments of nicotine dependence symptoms will be approximately 15-20 minutes/day. Our previous

research has obtained EMA compliance rates of >75% and found EMA reactivity to be nonexistent or small. We have extensive experience implementing and developing EMA programs and analyzing EMA data related to smoking behavior and anticipate no issues in carrying out this aspect of our proposal. Because prompts may occur at inconvenient times (e.g., driving), participants will be instructed that they can delay responding for up to 90 minutes, and they will receive a "missing assessment" SMS reminder if they fail to complete a daily or random assessment within 90 minutes of it being sent. The SMS/Qualtrics app will provide feedback on percentage of completed assessments, as well as compensation earned (see Recruitment and Retention Plan, above). We have successfully used this SMS/Qualtrics platform to collect similar EMA data in our current EC/VLNC product switching grant (2015-0638). Participants without a smartphone, or who would prefer not to use their own device, will be provided with a smartphone and service plan for the duration of the study. Given that 77% of adults own smartphones, as of 2016, we anticipate that relatively few participants will need a study smartphone.

**Assessment of product acceptability.** As part of Aims 1 & 2, product acceptability will be evaluated in terms of explicit product liking, perceived product harm, and implicit product liking (i.e., attitudes) at the end of each phase. Explicit product liking will be measured using Product Evaluation Scales (PES), which are modified versions of the Cigarette Evaluation Scale (CES). The CES is an 11-item questionnaire that evaluates the cigarette smoking experience in terms of satisfaction, tastiness, dizziness, ability to calm, concentration, wakefulness, reduction of hunger, nausea, irritability, enjoyment of sensations of smoke, and craving reduction. We will use 2 product-specific versions of the PES to evaluate CC and SREC product liking (with SRECs evaluated at weeks 4 & 6 only; see Appendix M).

To assess perceived product harm, we will administer modified Perceived Health Risk Questionnaires (PHRQs; see Appendix K) that will assess participants' beliefs about their risks of developing lung cancer, emphysema, bronchitis, other cancers, heart disease, risk of addiction, and stroke on a scale of 1 (very low risk of disease) to 10 (very high risk of disease). These scales will be modified so that participants will assess the perceived risks associated with their UB CCs and ECs (i.e., electronic cigarettes "in general") at each time point, and a SREC-specific version at weeks 4 & 6 only.

To assess implicit product liking, participants will complete 2 Implicit Association Tests (IAT) designed to evaluate attitudes towards CCs and ECs during each phase (see Appendix Q). The IAT has been used to evaluate attitudes toward consumer products and is comprised of two tasks. In the first task, participants are instructed to rapidly distinguish between two paired products and attributes (e.g., cigarettes + good vs. ECs + bad) using two assigned response buttons. In the second task, the pairings are switched. By calculating a standardized difference score between the reaction time differences, one can determine which products and attributes are more strongly associated in memory, thus determining whether an individual has a relatively more positive or negative attitude toward one product vs. the other. We have substantial previous experience with this task using established methods in our studies. We are currently using this task in our active EC study (2015-0638). For both products of interest, we created 24 pictures that minimize product branding, and the good and bad attribute words came from a previously published set from our lab. To score the IAT, we will use the standardized difference score (D) method. Each IAT product comparison will take approximately 8 minutes to complete.

COVID-19 adaptation: We will adapt the IAT to Qualtrics, an institutionally approved web-based platform, and will ask participants to complete the task electronically by accessing a hyperlink using a smartphone.

To assess product-specific expectancies (i.e., perceived outcomes of product use), we will administer the Brief Smoking Consequences Questionnaire-Adult (BSCQ-A) to assess CC-specific expectancies (see Appendix F) and the EC-specific Brief Smoking Consequences Questionnaire-Adult (EC-BSCQ-A) to assess EC-specific expectancies (see Appendix G). Both are 25-items questionnaires that assess beliefs (i.e., expectancies) about what happens when they smoke CCs (BSCQ-A) or use ECs (EC-BSCQ-A) on 10 scales, including Negative Affect Reduction, Stimulation/State Enhancement, Health Risks, Taste/Sensorimotor Manipulation, Social Facilitation, Weight Control, Craving/Addiction, Negative Physical Feelings, Boredom Reduction, and Negative Social Impression, using a 10-point Likert scale (0="completely unlikely" to 9="completely likely"). We will administer these questionnaires at all 4 phases and expect the EC-BSCQ-A to be sensitive to SREC dose (Aim 1) and both to be sensitive to gender differences in expectancies (Aim 2).

**Assessment of product reinforcement.** As part of Aims 1 & 2, we will assess CC and SREQ product relative reinforcing efficacy (RRE) using two separate product-specific purchase tasks (PT) at each in-person or virtual visit (with SRECs evaluated at weeks 4 & 6 only; see Appendices D and E). PTs are behavioral economic reward valuation tasks that have been used to assess the RRE of food, alcohol, illicit drugs, and nicotine products. PTs provide an estimate of how much a participant is willing to pay (i.e., its valuation) for a given product (UB, SREC) over a range of unit price intervals (\$0.01 to \$1,000). Responses will be used to compute five demand indices, including breakpoint (first price at which consumption goes to zero, i.e., unwilling to pay), demand intensity (consumption at the lowest price),  $O_{max}$  (maximum financial expenditure on the product),  $P_{max}$  (price at which expenditure is maximized), and elasticity of demand (sensitivity of product consumption to increases in cost). These relative values will be compared between CCs and SRECs to determine their RREs.

**Assessment of nicotine dependence symptoms.** As part of Aims 1 & 2, participants will complete questionnaires assessing nicotine dependence symptoms, including CC dependence (Fagerström Test for Cigarette Dependence [FTCD; formerly the FTND; see Appendix C]), EC dependence (Penn State Electronic Cigarette Dependence Index [PSECDI; see Appendix J]), nicotine withdrawal (Minnesota Nicotine Withdrawal Scale-Revised [MNWS; see Appendix H]), affect (Positive and Negative Affect Scales [PANAS; see Appendix I]), and craving to smoke (Questionnaire of Smoking Urges-Brief [QSU-Brief; see Appendix N]) at each study visit.

During all phases, SMS/Qualtrics will be used to collect 2 daily random smartphone EMA measures of nicotine dependence symptoms, including nicotine withdrawal, craving, and affect, based on 8 items from the QSU, PANAS, and MNWS. Further details about the 2 daily smartphone EMA measures, as well as the once daily assessments of product use, are described above in the "Assessment of product use" section.

**Assessment of respiratory and other symptoms.** We will also assess respiratory symptoms at each visit using the American Thoracic Society questionnaire (ATSQ). The ATSQ is an 8-item questionnaire that assesses symptoms including coughing, wheezing, phlegm production, shortness of breath. An email will be sent to project staff when a participant completes the ATSQ and has a total score of >3 on questions #4-8. Staff will assess symptoms with the participant at the next visit. If symptoms present prior to the start of study product (V0 or V1), staff will add the conditions to the medical history. If the elevated score presents while on study product, staff will assess changes in symptoms and severity and log an adverse event, if indicated.

Study Medical Monitor [name] will oversee the collection, review, and attribution of adverse events (AEs) in this study and will consult with [name] on respiratory-

related AEs, as needed. The physician may delegate to other members of the medical team the task of a preliminary review of the adverse event, attribution, and recommended action plan. The physician will then complete the final review of the adverse event, confirm attribution and sign off on the adverse events.

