## A. OBJECTIVES

The objective of this National Institutes of Health (NIH)-funded proposal is to characterize potential gender differences when switching from combustible cigarettes (CCs) to nicotine and placebo experimental electronic cigarettes, the National Institute on Drug Abuse's (NIDA) Standard Research E-Cigarettes (SRECs). We propose the following aims:

**Aim 1. To characterize the effects of switching to nicotine vs. placebo SRECs from CCs on product use, product acceptability, reinforcement, and nicotine dependence symptoms among adult daily CC smokers.** We hypothesize that nicotine-containing SRECs (SREC-NIC; 5%; ~59 mg/ml nicotine) will lead to decreases in CC-specific measures, decreases in withdrawal symptoms, and increases in electronic cigarette (EC)-specific use, acceptability, and reinforcement compared to placebo SRECs (SREC-PLA; 0 mg/ml nicotine). The primary outcome measure for Aim 1 will be CPD.

**Aim 2. To characterize the differences between male and female CC smokers when switching to nicotine vs. placebo SRECs from CCs on product use, product acceptability, reinforcement, and nicotine dependence symptoms.** We hypothesize that men, compared to women, will show more product use, acceptability, and reinforcement with SREC-NIC, relative to SREC-PLA, but that women will show overall less SREC use, and less CC reduction, than men. The primary outcome measure for Aim 2 will be CPD.

**Exploratory Aim: To characterize which factors moderate or mediate the effects of switching to nicotine and placebo SRECs from CCs among male and female CC smokers.** In an exploratory fashion, we will examine whether baseline factors, including prior EC exposure/ flavor preference, menthol CC preference, nicotine dependence, exposure (nicotine, cotinine, anabasine), hormonal contraception use, age, and race/ethnicity, moderate the Aims 1 & 2 hypotheses. We will also examine the mediating effects of product satisfaction, menstrual phase, and smartphone-collected withdrawal, craving, affect, product use on these hypotheses.

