**Hypothesis Testing: Aim 1. To characterize the effects of switching to nicotine vs. placebo SRECs from CCs on product use, product acceptability, reinforcement, and nicotine dependence symptoms among adult daily CC smokers.** Assessments will include: product use (CPD, number of EC vaping sessions, nicotine, cotinine, minor tobacco alkaloids); product acceptability (explicit product liking, implicit product liking, and perceived product harm); reinforcement (RRE) and nicotine dependence symptoms (withdrawal, craving, and affect). We hypothesize that SREC-NIC will lead to decreases in CC-specific measures (CPD, minor tobacco alkaloids, and CC dependence), decreases in withdrawal symptoms, and increases in EC-specific use, acceptability, and reinforcement compared to SREC-PLA. The primary outcome measure for Aim 1 will be CPD.

**Hypothesis Testing: Aim 2. To characterize the differences between male and female CC smokers when switching to nicotine vs. placebo SRECs from CCs on product use, product acceptability, reinforcement, and nicotine dependence symptoms.** This aim will examine the moderating role of gender on the impact of SREC type on the assessments described in Aim 1. We hypothesize that men, compared to women, will show more product use, acceptability, and reinforcement with SREC-NIC, relative to SREC-PLA, but that women will show overall less SREC use, and less CC reduction, than men. The primary outcome measure for Aim 2 will be CPD.

**Exploratory Aim: To characterize which factors moderate or mediate the effects of switching to nicotine and placebo SRECs from CCs among male and female CC smokers.** In an exploratory fashion, we will examine whether baseline factors, including prior EC exposure and prior flavor preference, menthol CC preference, nicotine dependence, baseline TNE, and race/ethnicity, moderate the Aims 1 & 2 hypotheses. We will also examine the potentially mediating effects of product satisfaction, hormonal contraception use, menstrual phase, and smartphone-collected withdrawal, craving, affect, product use on these hypotheses.

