**Consideration of Relevant Biological Variables.** We will recruit an equal number of male and female adult daily smokers for this study because gender differences form the main focus of this proposal. While biological sex is the primary independent variable, we will also account for other relevant biological variables, such as age, by including them as covariates of interest in our statistical models. We are using multilevel models to partially pool the estimate from each covariate toward the overall mean of all estimates. This is a natural away to account for multiple comparisons without sacrificing power (which we do in the case of Bonferroni correction). Each effect is shrunk toward the overall estimate. The higher the uncertainty of a specific effect the more it shrinks toward the overall estimate.

**Timetable.** After a 3-month study setup, we expect to enroll between months 6 and 20, at a rate of 10 subjects per month (see **Table 3**). The final participant session will be during month 22, and data analysis and initial manuscript drafting will occur by month 24.

**Future directions.** At the project's conclusion, we will be able to provide scientific information on gender differences in terms of the extent to which the NIDA SREC is used and accepted by adult CC smokers, which would indicate whether it could serve as a good model of future EC research. We will also identify factors that moderate or mediate the effects of switching to nicotine and placebo SRECs from CCs. Our next steps will be to submit proposals

hormonal contraception. However, we will capture self-report of both factors and use them as moderators (hormonal contraceptive use) and mediators (menstrual phase) as part of the exploratory aim.

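### Menstrual phase is planned as a mediator of the SREC effect, but no path from product to cycle phase is proposed, so this exploratory mediation test is null by design

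*Combined protocol and SAP*

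**What the plan says.** Four places give menstrual phase a role in the analysis, and all four make it a mediator.

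- A. Objectives, Exploratory Aim: "We will also examine the mediating effects of product satisfaction, menstrual phase, and smartphone-collected withdrawal, craving, affect, product use on these hypotheses".
- Measures, under demographics and health history: "we will examine these factors as potential mediators in our analyses (Exploratory Aim". The factors meant are menstrual phase and hormonal contraception.
- Statistical Approach & Expected Outcomes, Exploratory Aim: "We will also examine the potentially mediating effects of product satisfaction, hormonal contraception use, menstrual phase".
- Potential Problems & Alternative Strategies, which separates the two roles explicitly: "use them as moderators (hormonal contraceptive use) and mediators (menstrual phase".

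Measures describes the variable as "menstrual phase (estimated from the start date of the last menstrual period) in premenopausal women", self-reported at visits 0 to 3. There is no hormone assay. The reason for interest is that withdrawal may influence switching. "Both being in the luteal phase, compared to follicular phase" and use of hormonal contraception are both said to increase withdrawal.

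Hormonal contraception does not keep one role. It is a moderator in Objectives and in Potential Problems, and a mediator in Measures and in the Statistical Approach.

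**The concern.** A mediator lies on the path from treatment to outcome: product changes the mediator, and the mediator changes CPD or withdrawal. For menstrual phase the first link is missing. The product given in each two-week period is set by a randomised order, and cycle phase is read from the date of the last period. The plan's own rationale runs from cycle phase to withdrawal to switching. That puts phase upstream and makes withdrawal the candidate mediator.

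The mediators are meant to bear on the hypotheses of both Aims 1 and 2. For Aim 2 there is a second obstacle: phase has no value in men, so it cannot carry a difference between men and women in the product effect.

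What is at stake is interpretation. The test will almost always return a null whether or not cycle phase affects smoking. In a trial about gender differences, that null could be reported as evidence that phase is unimportant. No analysis of whether the SREC response differs by cycle phase is prespecified.

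**Working it through.** The misclassification follows from reading the sections together and needs no arithmetic. The calculations show what the planned test would return and how much the primary outcome is affected.

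**Inputs from the plan.** Product order is randomised 1:1 and stratified by gender; each product is used for 2 weeks (Procedures; Potential Problems). CPD comes from a daily diary, with TLFB as back-up (Assessment of product use). The analysed sample is 140, with 80% power for a 1.75 CPD main effect and a 3.5 CPD gender interaction (Power and Sample Size).

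**Assumptions not in the plan.** Two-sided alpha 0.05; a 28-day cycle with a 14-day luteal half and a random start day; a luteal effect of 0 to 3 CPD; 70 cycling women (half of 140, an upper limit) or 40.

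**1. Implied SD of a person's SREC-NIC minus SREC-PLA difference.** The plan states no SD or alpha, so its 80% power cannot be reproduced independently. Working backwards:

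SD = 1.75 × √140 / (1.960 + 0.842) = 7.39, and SD² = 54.6.

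The interaction figure gives the same value: 3.5 × √140 / (2 × 2.802) = 7.39.

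**2. Indirect effect.** Write it as a × b, where a is the effect of product on luteal share and b the effect of luteal share on CPD. Randomised order gives an expected a of 0, provided the product does not alter cycle timing, so the expected a × b is about 0 whatever b is. A simulation of 4,000 trials per setting, with CPD averaged over each two-week period, gave the following for 70 cycling women:

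| Luteal effect (CPD) | Mean a × b | SD of a × b | Sobel test rejects | SE of product effect, unadjusted | SE, adjusted for luteal share |
|---|---|---|---|---|---|
| 0 | -0.002 | 0.10 | 0.03% | 0.88 | 0.89 |
| 1 | 0.001 | 0.13 | 0.03% | 0.89 | 0.89 |
| 2 | 0.002 | 0.17 | 0.08% | 0.88 | 0.88 |
| 3 | 0.000 | 0.23 | 0.25% | 0.91 | 0.89 |

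With 40 cycling women the mean of a × b stayed within 0.006 of zero and the Sobel test rejected in at most 0.13% of runs. Across all settings the mean of a lay between -0.003 and 0.001, and its own test rejected in 5% to 6% of runs, close to the nominal 5%. A true luteal effect of 3 CPD is therefore practically invisible to the planned mediation test.

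**3. Effect on the CPD contrast.** With two consecutive 14-day periods in a 28-day cycle, the luteal shares of the two periods sum to 1. Their difference is about uniform on -1 to 1, with variance 1/3 (simulated 0.33). A luteal effect of d CPD adds about d²/3 to the variance of a cycling woman's difference:

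- d = 1: 0.333 / 54.6 = 0.6%
- d = 2: 1.333 / 54.6 = 2.4%
- d = 3: 3.000 / 54.6 = 5.5%

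If 40 of 140 participants cycle, the largest figure averages 5.5% × 40 / 140 = 1.6% over the sample. As the table shows, adjustment changes the standard error by about 0.02 CPD at most. The product effect was unbiased with and without adjustment.

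**The case against.** The strongest reply concerns the consequences.

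- **Scope.** Menstrual phase is one of several candidates in an aim labelled exploratory, and the plan repeatedly calls these factors exploratory. This stands: the CPD analyses for Aims 1 and 2 are untouched.
- **Is a useful covariate wasted?** A reader might infer so, but the documents do not support it. The paragraph on relevant biological variables promises covariates and gives age only as an example, and nothing bars the use of phase. All that can be said is that no covariate or moderator role is prespecified for it by name.
- **Does omitting phase leave substantial noise in CPD?** A reader might take the two product visits, 14 days apart, as opposite halves of the cycle and count the full squared shift: 1, 4 and 9 over 54.6, or 1.8%, 7.3% and 16.5%. That would suit an outcome taken only at those visits. CPD comes from daily records over each period, so d²/3 applies and the figures are about a third as large.
- **Is a spurious positive finding likely?** No. The Sobel test rejects in under 0.3% of runs. The realistic result is an uninformative null.
- **Is it impossible for the product to affect the cycle?** The documents do not say so; they simply offer no such path.

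None of this defends the mediator label. The plan neither justifies it nor gives a reason that fits it.

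**Conclusion.** The point holds for the role given to menstrual phase. In all four places phase is assigned a role that the plan's own rationale contradicts, and for Aim 2 it is undefined in half the sample. The planned mediation test has an expected indirect effect of about zero and cannot show whether cycle phase matters. This rests on randomised order and on the product not changing cycle timing.

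The size is modest and confined to the Exploratory Aim. The primary CPD contrasts are unbiased either way. Any precision gain from adjustment is small: phase adds about 0.6% to 5.5% to the variance of a cycling woman's difference for an assumed 1 to 3 CPD shift, a 28-day cycle and two-sided alpha of 0.05. The case for change is that the analysis cannot inform its aim. It is not that Aims 1 and 2 are compromised.

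The conflicting roles of hormonal contraception are a separate inconsistency and can be settled in the same edit.

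**What to change.** In the Exploratory Aim under Objectives, the Measures text, the Exploratory Aim under Statistical Approach, and Potential Problems & Alternative Strategies:

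1. Remove menstrual phase from the mediators. Prespecify it as a time-varying covariate and as a phase-by-SREC-type moderator, in premenopausal women not using hormonal contraception.
2. Label that analysis exploratory and state that its power is limited, because the size of the subgroup is unknown and phase is self-reported.
3. Keep mediation for variables the product can change: satisfaction, withdrawal, craving and affect.
4. Give hormonal contraception one role, moderator, in all four places.

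The cost is wording and a few terms in an exploratory model. Phase and contraception are already recorded at visits 0 to 3 and CPD daily, so no new data are needed. The change is best made before outcome data are examined.
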